## **MusiQoL Questionnaire**

The effect of MS on quality of life (QOL) will be measured using the Multiple Sclerosis International QoL (MusiQoL) questionnaire to reflect subject's view points on the impact of MS in their daily lives.

MusiQoL Overall and MusiQoL dimensions scores will be derived according to MusiQoL scoring algorithm (Refer Appendices). Descriptive statistics will be presented for the MusiQoL overall score at baseline, Month 6, and Month 12, and change from baseline at Months 6 and 12 from Safety Analysis set. Same descriptive statistics will be presented for the following MusiQoL dimensions.

- Activities of Daily Living (ADL)
- Psychological Well-Being (PWB)
- Relationships with friends (FR)
- Relationships with family (FA)
- Self-Esteem (SE)
- Relationship with Health Care System (RHCS)
- Sentimental & Sexual life (SSL)
- Coping (COP)
- Rejection (REJ)

MusiQoL Overall score = Sum of all MusiQoL dimension scores / No. of MusiQoL dimensions.

MusiQoL Overall score will be computed as the mean of the dimension scores, when none of the 9 dimension scores is missing.

A paired two-sided t-test will be used to test the null hypothesis that there is no difference in the MusiQoL Overall and dimensions scores between 6, 12 months and Baseline.

### **Reason(s) for discontinuation of Prior MS therapy:**

The qualitative variables

- Reason(s) for discontinuation of prior MS Therapy (Adverse event / Lack of efficacy /Other)

will be summarized by prior MS Therapy categories and overall as number and percentage from Safety Analysis Set.

### **Additional Secondary Endpoints Analyses:**

#### **Correlation between TSQM v II and ARR; TSQM v II and Adherence**

Correlation between TSQM v II (Global satisfaction score) and ARR; TSQM v II (Global satisfaction score) and Adherence will be evaluated by using either Pearson's correlation procedure or Spearman's rank correlation procedure based on normality of the data from Safety Analysis Set.

The results from the correlation analysis will be presented in the table with correlation coefficient (r), 95% CI and p-value.

#### **TSQM v II and reason for discontinuation**

The qualitative variable

- Global satisfaction score

will be summarized using descriptive statistics by reasons for discontinuation i.e. Adverse event, Lack of efficacy and others from Safety Analysis Set.

#### **Correlation between MusiQoL and ARR; MusiQoL and Adherence;**

Correlation between MusiQoL (Overall Score) and ARR; MusiQoL (Overall Score) and Adherence will be evaluated by using either Pearson's correlation procedure or Spearman's rank correlation procedure based on normality of the data from Safety Analysis Set. The results from the correlation analysis will be presented in the table with correlation coefficient (r), 95% CI and p-value.

#### **MusiQoL and reason(s) for discontinuation**

The qualitative variable

- MusiQoL Overall score

will be summarized using descriptive statistics by reasons for discontinuation i.e. Adverse event, Lack of efficacy and others from Safety Analysis Set.

### **Correlation between TSQM v II subscales and adherence**

Correlation between TSQM v II Subscales (Effectiveness, Side Effects and Convenience) and Adherence will be evaluated by using either Pearson's correlation procedure or Spearman's rank correlation procedure based on normality of the data from Safety Analysis Set.

The results from the correlation analysis will be presented in the table with correlation coefficient (r), 95% CI and p-value.

### **TSQM v II subscales and reason for discontinuation**

The quantitative variables

- Effectiveness
- Side Effects
- Convenience

will be summarized using descriptive statistics by reasons for discontinuation i.e. Adverse event, Lack of efficacy and others from Safety Analysis Set.

### **TSQM v II subscales at Baseline and after 6 and 12 months of Rebif treatment**

TSQM v II dimensions scores will be derived according to TSQM v II Scale Scoring Algorithm (Refer Section 16.1) mentioned below.

- Effectiveness
- Side Effects
- Convenience

will be summarized for baseline, Month 6, and Month 12, and change from baseline at Months 6 and 12 using descriptive statistics from Safety Analysis set.

A paired two-sided t-test will be used to test the null hypothesis that there is no difference in the TSQM v II dimensions scores between 6, 12 months and Baseline.

The corresponding 95% two-sided CI will be presented.

**Association between number of relapses and treatment adherence:**

Univariate negative binomial regression analysis will be performed to identify the factors contributing to number of relapses. The number of relapses as dependent variable and following variables will be the independent variables for the regression analysis.

- Adherence (%)
- Log (Time on Study (days))
- Age (years)
- Sex (male/female)
- Number of MS relapses within 24 months prior to written informed consent

Further, multiple negative binomial regression analysis will be performed for all independent variables listed above to identify the factors contributing to number of relapses from safety analysis set. All independent variables with a p-value  $\leq 0.15$  in univariate negative binomial regression analysis only will be considered for multiple negative binomial regression analysis. Method of regression will be the forward stepwise addition method.

Diagnosis of Multicollinearity:

In SAS version 9.1.3, the variance inflation factor (vif) option will be used to detect the multicollinearity. The variables whose VIF values are greater than 10 may merit further investigation. Tolerance, defined as  $1/VIF$ , is used to check on the degree of collinearity. A tolerance value  $< 0.1$  is comparable to a VIF of 10. It means that the variable could be considered as a linear combination of other independent variables. The tol option on the model statement gives these values.

Further, the independent variables which are having  $vif < 10$  and  $tol > 0.1$  will be included in the final model.

The results of univariate and multivariate negative binomial regression analysis will be reported with the following items

- Estimate

- Standard Error
- 95% CI
- P-value

The above mentioned negative binomial regression analysis will be performed when the outcome variable is over-dispersed, i.e., when the situation like data show extra variation that is greater than the mean. Otherwise, Poisson regression analysis will be performed as an alternative method.

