## 16.2 Secondary Endpoint Analyses

### Annualized Relapse Rate (ARR):

The quantitative variables,

- Annualized Relapse Rate before study entry
- Number of relapses during the study
- Annualized Relapse Rate on study

will be summarized for prior MS Therapy categories and overall using descriptive statistics from Safety Analysis Set.

Annualized Relapse Rate before study entry = (No. of Relapses within 24 months prior to written informed consent / (30.4375\*24)) \* 365.25

Annualized Relapse Rate on study = (Sum of No. of Relapses at month 6 and month 12/ Time on Study) \* 365.25

where,

Time on Study (days) = (Date of Study Completion or Date of study discontinuation - Date of first Rebif administration +1)

95% Confidence Interval (CI) will also be provided for Annualized Relapse Rate before study entry and on study.

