#### **Adherence Evaluation:**

Adherence (%) will be calculated for each subject as 100 x the number of injections the subject administered divided by the expected number of injections over 6 or 12 Months. If the subject terminates earlier than 12 months, the expected number of completed injections will be based on the subject's time on study.

The quantitative variable

- Adherence (%)

will be summarized for month 6 and month 12/End of treatment using descriptive statistics from Safety Analysis Set.

Adherence (%) = (No. of injections the subject administered / Expected No. of injections over 6 or 12 Months) x 100.

Number of injections the subject administered = Expected number of injections over 6 or 12 Months - Total No. of estimated missed injections since baseline visit.

The expected number of injections 3 times weekly (i.e. 3\*24 weeks (6 months) = 72 expected injections over 6 months and 144 expected number injections over 12 months).

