### **16.3 Other Endpoint Analyses**

#### **Relapse Assessment:**

The qualitative variables

- Subject experienced any MS relapses since last visit (Yes / No)

will be summarized for month 6, month 12 using descriptive statistics from Safety Analysis Set.

The quantitative variable

- No. of Relapses since last visit

will be summarized for month 6, month 12 as number and percentage from Safety Analysis Set.

Listing will be provided for Relapse assessment.

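### The relapse regression uses adherence from the same period as the relapses, so its coefficient cannot show that adherence contributes to relapses

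*SAP*

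**What the plan says.** In SAP section 16.2, under the association between relapses and adherence, the model is set up as follows: "The number of relapses as dependent variable and following variables will be the independent variables for the regression analysis". Adherence (%) heads the list of independent variables, followed by log time on study, age, sex and relapses in the 24 months before consent. The stated aim is that the regression "will be performed to identify the factors contributing to number of relapses". Variables with p ≤ 0.15 in single-variable models go forward to stepwise selection.

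The two quantities are built as follows.

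- **Relapses.** The on-study rate in section 16.2 uses "Sum of No. of Relapses at month 6 and month 12/ Time on Study", so relapses are counted over the whole study.
- **Adherence.** Injections administered are "Expected number of injections over 6 or 12 Months - Total No. of estimated missed injections since baseline visit". The expected numbers are "72 expected injections over 6 months and 144 expected number injections over 12 months". For patients who stop early, "the expected number of completed injections will be based on the subject's time on study". The result "will be summarized for month 6 and month 12/End of treatment using descriptive statistics from Safety Analysis Set".

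The section does not say which of the two adherence values enters the model. It does not lag adherence, date missed injections against relapse onset, or set aside injections missed after a relapse. Reasons for missed injections are tabulated only, and relapse is not a listed reason.

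Two other places set the status of the analysis. The endpoint list in section 6 calls it an association, and section 11 makes all tests exploratory with descriptive p-values.

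**The concern.** A predictor that is meant to explain an event should be measured before it. Here the predictor is totalled over the period in which the events occur. A patient who relapses and skips injections for a while ends the year with lower adherence and a higher relapse count, whichever came first. The resulting negative association has the sign one would expect if good adherence prevented relapses.

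The bias affects the estimate and its confidence interval as well as the p-value. It also feeds the p ≤ 0.15 screen, so an adherence term driven by relapses can enter the final model. Described as a contributing factor, it would be read in the wrong direction.

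**Working it through.** **Figures in the plan.** The SAP gives no figure for this regression. Its size is taken from section 7. The paired formula reproduces that number: n = [27.5 × (1.960 + 1.036) / 8]² ≈ 106. This serves only as the number of patients in the simulations.

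**The mechanism in one patient.** Take 144 expected injections and assume 7 habitual misses. Without a relapse, adherence is (144 − 7)/144 = 95.1%. With one relapse that costs three injections (one week at three per week), it is (144 − 10)/144 = 93.1%. The relapse has moved the predictor by 3/144 = 2.1 points. Six lost injections move it by 6/144 = 4.2 points.

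**Simulations with no effect of adherence on relapses.** The following are assumptions, as the SAP gives none of them: the relapse rate, the spread of habitual missing, and the number of injections lost per relapse.

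- *A*: equal relapse risk, rates 0.2 and 0.4 per year, habitual non-adherence half-normal with SD 10 points, Poisson regression.
- *B*: a separate run with 106 patients and rates 0.2 to 0.4 per year. This gives the headline range. A repeat with the half-normal spread of A, with relapse risk either equal or gamma-varying, and with the SAP's choice between negative binomial and Poisson, gave rates of similar size.
- *C*: gamma-varying risk (dispersion 1), the SAP's negative binomial or Poisson rule, 400 runs per setting, rate 0.3 per year, with 7 or 14 of 144 injections missed habitually.

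Share of trials with p < 0.05 for adherence:

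| Injections lost per relapse | A | B | C, 7 habitual | C, 14 habitual |
|---|---|---|---|---|
| 0 | 5% | 4–7% | 3% | 4% |
| 1 | 8–10% | 10–15% | 10% | 7% |
| 3 | 32–57% | 34–75% | 64% | 22% |
| 6 | 84–98% | 88–100% | 98% | 72% |

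In C the median rate ratio per 10 points higher adherence, where the truth is 1, was 1.01, 0.77, 0.47 and 0.32 down the table with 7 habitual misses, and 1.01, 0.92, 0.78 and 0.66 with 14. Over rates 0.2 to 0.5 and both habitual levels, three lost injections gave 13–88% significant results and passed the p ≤ 0.15 screen in 30–96%. Six gave 45–100% significant results. Some negative binomial fits in C gave no standard error, and these figures use converged runs only (64–100% of runs, depending on the setting).

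**Does ordering in time help?** Relapses are recorded as "No. of Relapses since last visit" at Months 6 and 12, and adherence is available at Month 6. Relapses after Month 6 can therefore be regressed on adherence up to Month 6. With varying relapse risk, ordering alone is not enough, because relapse-prone patients have both early lost injections and later relapses. False positives reached 19% in one set of runs and 32% in another. Adjusting for relapses up to Month 6 brought them to 4–8% and about 2–6% respectively. In the second set, runs that did not converge counted as non-significant, so its rates may be slightly low.

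**What that model can show.** Expected relapses after Month 6 are 106 × 0.2 × 0.5 ≈ 11 to 106 × 0.4 × 0.5 ≈ 21. At an assumed true rate ratio of 1.5 per 10 points lower adherence, power is roughly 14–21%.

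**The case against.** The strongest reply is that the plan makes no causal claim. The endpoint and the section heading both speak of an association, all p-values are descriptive, and the contributing-factor wording covers age, sex and prior relapses as much as adherence. It may be no more than stock regression language. This stands, and it lowers the weight of the point. It does not justify keeping the wording, because a descriptive p-value does not remove bias from the estimate beside it.

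Second, nothing in the SAP says that relapses interrupt injections. That is also right. With no injection lost there is no bias, and with one it is small. The large rates depend on losses of about a week or more per relapse.

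Third, the section does not fix which adherence value is used. The cumulative value at Month 12 or end of treatment is the natural reading. Month 6 adherence set against all on-study relapses would still overlap with those of the first six months.

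A reader might go further and infer that the trial will report a spurious adherence effect, or that the time-ordered model should replace the planned one as the interpretable analysis. The documents support neither. The loss per relapse is unknown, and the ordered model has too few events to carry a conclusion.

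**Conclusion.** The point holds in limited form. Adherence and relapses share one observation window with no time ordering, so the coefficient cannot separate adherence affecting relapses from relapses affecting adherence. The directional wording goes beyond what the analysis can show.

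The size depends on the unquantified number of injections lost per relapse. At 106 patients and 0.2 to 0.4 relapses per year, the false-positive rate runs from nominal (4–7%) with none lost to 88–100% with six. With more habitual missing the rates are lower, as the last column of the table shows. This is a limitation of an exploratory secondary analysis that is cheap to correct. It does not touch the primary endpoint.

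**What to change.** In SAP section 16.2, under the association between relapses and adherence:

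1. Replace *contributing to* by *associated with* wherever the aim is stated. Name the adherence value that enters the model. Add that the 12-month adherence coefficient cannot separate an effect of adherence on relapses from an effect of relapses on adherence.
2. Add one sensitivity model: relapses from Month 6 to Month 12 regressed on adherence from Visit 1 to Month 6. Adjust it for relapses from Visit 1 to Month 6 and for relapses in the 24 months before consent. Use log time at risk after Month 6 as offset, and include patients still under observation at Month 6. Keep the planned 12-month model as a descriptive association.

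The cost is a few lines of text and one model on data already collected. The sensitivity model will be imprecise, with about 11–21 expected relapses, and the SAP should say that a null result from it is not evidence of no association. Adjusting for first-half relapses may also remove part of any true early effect of adherence.

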	
from Baseline to Month 6 and to Month 12.
 
Secondary Endpoints:
 
 
• ARR (after 12 months of Rebif treatment)
 
• Adherence (after 6 and 12 months of Rebif treatment)
 
• MusiQoL (compare Baseline with after 6 and 12 months of Rebif treatment)
 
• Reason/s for discontinuation of initial MS treatment (oral or injectable).
 
 
Additional Secondary Endpoints:
 
 
• Correlation between TSQM v II and ARR; TSQM v II and adherence; TSQM v II and reason for discontinuation
 
• Correlation between MusiQoL and ARR; MusiQoL and adherence; MusiQoL and reason for discontinuation
 
• Correlation between TSQM v II subscales and adherence
 
• Correlation between TSQM v II subscales and reasons for discontinuation
 
• Difference between TSQM v II subscales at Baseline and after 6 and 12 months of Rebif treatment
 
• ARR before study entry compared to ARR at study end
 
• Association between ARR and treatment adherence.
 

Study Design
	
This is a prospective, multicenter, open label, uncontrolled, non-interventional, single arm study to measure treatment satisfaction of RRMS patients on Rebif after discontinuing initial first-line treatment.
 
This study consists of three visits:
 
 
• Visit 1: Baseline
 

	
 
• Visit 2: Month 6
 
• Visit 3: Month 12
 
 
This study will enroll RRMS patients who have discontinued their oral or injectable first-line MS medication and have decided to initiate subcutaneous Interferon beta-1a (IFN <math>\beta</math> -1a) (Rebif) treatment before Baseline measurements. MusiQoL and TSQM v II will be measured at Baseline, Month 6 and Month 12. Relapses and adherence will be assessed at Month 6 and Month 12. Adherence to Rebif therapy will be collected electronically using RebiSmart 2.0.
 
Since this is a non-interventional study, there will not be any study required clinical interventions and laboratory assessments.

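### The relapse–adherence regression has no exposure offset, can screen out adherence or follow-up time, and gives conflicting rules for its multiple model

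*SAP*

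**What the plan says.** Section 6 of the SAP lists among the additional secondary endpoints "Association between ARR and treatment adherence". ARR is a rate: Section 16.2 (Annualized Relapse Rate) divides relapses by Time on Study.

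The regression for this endpoint is in Section 16.2, under the heading on number of relapses and treatment adherence. It states: "The number of relapses as dependent variable and following variables will be the independent variables for the regression analysis". The list holds adherence (%), log of time on study, age, sex and relapses in the previous 24 months. No term is called an offset. Each variable has its own univariate model.

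For the multiple model, the section gives these rules in turn:

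- a rule on scope: "multiple negative binomial regression analysis will be performed for all independent variables listed above"
- a p-value screen with 0.15 as its limit: "in univariate negative binomial regression analysis only will be considered for multiple negative binomial regression analysis"
- a selection procedure, for which no entry level is given: "Method of regression will be the forward stepwise addition method"
- a collinearity check, by which variables with a variance inflation factor (VIF) below 10 and tolerance above 0.1 "will be included in the final model"

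For subjects who stop early, Time on Study is "Date of study discontinuation - Date of first Rebif administration +1". For completers the end date is study completion. The relapses counted are those recorded at Months 6 and 12.

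**The concern.** There are three linked faults and one that affects the remedy.

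1. **The rate is not modelled as a rate.** The univariate adherence model has no time term, so a patient seen for two months counts the same as one seen for twelve. Where time does enter, its coefficient is free.
2. **The screen applies to the wrong variables.** A p-value screen may be defended for nuisance covariates. Here it also covers adherence, which the endpoint is about, and time, which turns the count into a rate. Neither is exempt.
3. **The content of the multiple model is not fixed.** Two programmers could follow the same text and fit different models.
4. **Time may not match the count.** Section 6 allows up to 6 months of Rebif before Visit 1, so time counted from first Rebif can start before relapse counting does.

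At stake is the one planned estimate of how relapse rate relates to adherence. The adjusted version may not exist, and the version that is always reported ignores time observed.

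**Working it through.** **The plan's own figures.** The SAP gives no planning figure for this regression. Its sample size (Section 7) reproduces: (27.5 × (1.960 + 1.036) / 8)² = 106.1, and 106 / 0.80 = 132.5, hence 133. The check below takes 133 patients and about 20% leavers from there.

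**The model the endpoint calls for.** With T the time over which relapses are counted and A adherence, E(relapses) = T × exp(b0 + b1·A), so

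log E(relapses) = log T + b0 + b1·A.

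The coefficient of log T is 1 by definition. If log T is left out, b1 also absorbs any association between A and log T. There is no bias if that association is absent.

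**What each sentence produces.**

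| Rule followed | Multiple model |
|---|---|
| All listed variables | All five terms, time coefficient estimated |
| Univariate p ≤ 0.15, then forward addition | Any subset, possibly without adherence or time; entry level unknown |
| VIF and tolerance sentence, read literally | Every non-collinear variable, including those screened out |

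**Simulation inputs (all assumed except 133 and about 20%).** Relapse rates 0.2, 0.3 and 0.5 per year; rate ratio 1.0 or 0.80 per 10 adherence points; adherence 100 × Beta(8, 1.5); gamma frailty with shape 2; exit uniform on days 15–350; Rebif before Visit 1 uniform on 0–182 days. Dropout was random, linked to adherence (odds ratio 2 or 3 per 10 points lower), or relapse-triggered (half leave within 30 days of the first relapse, plus 10% random). Leavers before day 182 were either in or out of the model. That is 3 × 2 × 4 × 2 = 48 scenarios, with 1,500 runs each, fitted by negative binomial maximum likelihood (Poisson at zero dispersion).

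**Screen at p ≤ 0.15, true ratio 0.80.** Adherence passes as follows (all leavers contribute, Wald test):

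| Dropout | 0.2/yr | 0.3/yr | 0.5/yr |
|---|---|---|---|
| Random | 43% | 53% | 66% |
| Odds ratio 2 | 28% | 34% | 41% |
| Odds ratio 3 | 22% | 25% | 30% |

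- With random dropout adherence therefore fails in 57%, 47% and 34%. The range is 34–59% over all cases with dropout unrelated to adherence, and 34–80% over all patterns.
- Log time, counted from first Rebif ever, passes in 21–67% if leaving is unrelated to relapses and 78–87% if relapses trigger leaving (all contribute). With leavers before Month 6 out, these become 12–18% and 39–50%.
- Adherence and log time (from Visit 1) both pass in 1–54%.

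**Univariate adherence ratio, true value 0.80.**

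| Dropout | No offset | Offset |
|---|---|---|
| Unrelated to adherence | 0.80–0.81 | 0.80–0.81 |
| Linked, all leavers contribute | 0.86–0.90 | 0.80–0.82 |
| Linked, leavers before Month 6 out | 0.82–0.85 | 0.80–0.82 |

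Cross-check: with no true effect, linked dropout and no offset, the ratio is 1.07–1.12 (all contribute) or 1.03–1.04 (not before Month 6). Then 0.80 × 1.07 to 0.80 × 1.12 = 0.86–0.90, and 0.80 × 1.03 to 0.80 × 1.04 = 0.82–0.83, which agrees with the large-sample limits of 0.86–0.89 and 0.82–0.83.

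Power in the linked cases is 9–24% without an offset against 22–44% with one (all contribute), and 16–34% against 20–41% (not before Month 6).

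**All five variables in the model.** The adherence ratio is 0.79–0.81, or 0.83–0.84 if relapses trigger leaving and all contribute. The time coefficient, which should be 1, has a 5th–95th percentile range of 0.3–3.4 at 0.5 per year, and a median of −0.3 to −0.7 if relapses trigger leaving.

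**Other assumptions.** With rates of 0.2 or 0.4, dispersion 1, likelihood-ratio tests and leavers 15 adherence points lower, the mean log ratio without time is −0.07 to −0.08 (ratio about 0.92–0.93), against −0.21 to −0.22 with an offset and a true −0.223. Across that set, with leavers either equal or 15 points lower in adherence, adherence fails the screen in 62–79% of trials at a true ratio of 0.80.

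**Time on Study.** If the start is the first Rebif dose ever, a completer with 6 earlier months has (12 + 6) / 12 = 1.5 times the period over which relapses are counted.

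**The case against.** The strongest points on the other side are these.

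- *Exposure is not ignored.* Log time is a candidate, and with all five terms in the model the adherence ratio is close to the truth. This is correct, but it helps only if that reading is adopted. The univariate estimate stays unadjusted under every reading.
- *The bias needs assumptions.* It arises only if low adherers leave early, and it shrinks if leavers before Month 6 have no data. Section 6 schedules relapse and adherence assessment at Months 6 and 12, and Section 11 does not replace missing data, so that is possible. Section 16.2 also scales expected injections to time on study, so leaving early does not itself lower adherence. All of this stands.
- *The screening failures are not caused by the missing offset.* They reflect few relapses in 133 patients. With random dropout, adherence passes in 45/53/62% without an offset and 43/52/63% with one, at 0.2/0.3/0.5 per year. This stands: the offset and the retention of adherence are separate repairs.
- *A univariate adherence estimate is always reported.* It is; only the adjusted estimate can be absent.
- *The rules can be read as successive filters.* They can, but the first sentence still conflicts with the second, the entry level is still missing, and that reading is the one that lets adherence and time drop out.
- *The start date is ambiguous rather than wrong.* Agreed. Section 6 (Data Analysis) speaks of a dose after enrolment and Section 15 uses a different term for the start of therapy. The factor of 1.5 is the extreme case.

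**Conclusion.** The concern holds. Three points rest on the text alone: there is no offset, neither adherence nor time is protected from the screen, and the sentences on the multiple model disagree.

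The size of the harm depends on assumed relapse rates, dispersion, adherence distribution and dropout pattern. Under those assumptions, losing the adjusted adherence estimate is a common outcome, at roughly one trial in three or more even when dropout is unrelated to adherence. Bias in the univariate estimate is conditional: none if dropout is unrelated to adherence, and a true 20% reduction per 10 points shown as 10–18% if it is strongly linked.

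Section 11 makes all tests exploratory with descriptive p-values, this is an additional secondary endpoint, and the primary TSQM analysis is untouched. It should be fixed, but it does not threaten the main result.

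**What to change.** Amend Section 16.2 as follows.

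1. Use log of the time over which relapses are counted as an offset, coefficient fixed at 1, in every univariate and multiple model (negative binomial or Poisson). Remove it from the candidate list.
2. Keep adherence in the multiple model by design, whatever its univariate p-value.
3. Replace the conflicting sentences with one rule. If selection is kept for age, sex and prior relapses, state the entry level and say what the collinearity check may remove. Pre-specifying these three covariates instead is simpler but optional.
4. In the Time on Study definition, state which Rebif date is meant and align the period with the one over which relapses are counted.
5. Report the adherence rate ratio with its 95% CI.

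The cost is SAP wording and one model option. No new data are needed.
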